2.2. Pooling Algorithm for Analysis Centers

There are two sites in this study and the data from the two sites involved will be pooled for analysis.

2.3. Analysis Sets

Vaccination assignment will follow the "as treated" principle. That is, participants will be analyzed according to the actual intervention received.

2.3.1. Full Analysis Set (FAS)

The full analysis set will include all participants with at least one study intervention administration documented.

2.3.2. Per Protocol Immunogenicity Population (PPI)

The per-protocol immunogenicity population will include all randomized and vaccinated participants for whom immunogenicity data are available excluding participants with major protocol deviations expecting to impact the immunogenicity outcomes (eg, missed Dose 2 vaccination, natural infections, etc.). In addition, the following will be considered for the immunogenicity analysis:

 Immunogenicity samples of participants obtained after missed doses (or out-of-window Dose 2 vaccinations), samples obtained after natural infection (if applicable) or samples obtained outside the protocol-defined window will be excluded in graphs and tables showing descriptive statistics. These measurements will however be shown in listings, together with the indication that they are not used in the analysis.

- The immunogenicity analysis will be repeated on the full analysis set to evaluate the robustness of the analysis results, if more than 10% of participants from the full analysis set are excluded from the per protocol immunogenicity population.

2.4. Definition of Subgroups

There are 2 age groups (ie, ≥ 4 to ≤ 8 months, and ≥ 8 to ≤ 12 months of age) in this study and the study data (participant information, safety and immunogenicity) will be presented by these age groups. The study data will also be presented pooled over these 2 age groups.

3. INTERIM ANALYSIS AND DATA MONITORING COMMITTEE REVIEW

The primary interim analysis will be done when all participants have completed the 12 months post-dose-1 visit or left the study (ie, completion of the main study), and the clinical database is locked and unblinded. This analysis will include all available data up to the 12 months post-dose-1 (D365) visit.

For the main study, an independent data monitoring committee (IDMC) will be instituted prior to the start of the study. The IDMC will periodically review safety data to ensure progressive safety of the participants. Enrollment of participants will start with vaccination of a sentinel cohort of 16 infants before exposing the remainder of the infants to the study intervention. The IDMC will review data of the sentinel cohort. Progression to the enrolment of the remainder of the participants will be based on the favorable IDMC review of the safety data of the sentinel cohort of 16 infants. Ad-hoc IDMC meetings may also be requested via the sponsor for any single event or combination of multiple events which are considered to jeopardize the safety of the participants. See the IDMC charter² and the associated SAP³ for further details.

For all cases, the data package and analysis results that contained any piece of unblinding information will be kept in a strictly confidential place, with access for IDMC and the independent statistical support group members only until unblinding of the study by the sponsor.

The final analysis will be performed when all participants have completed the last study-related visit or discontinued earlier.

4. SUBJECT INFORMATION

Participant information will be shown for the full analysis set. In general, the data will be presented by age group (in months) and intervention arm. This information will be shown for the main study, as well as for the extension phase. The extension phase consists of all participants in the control arm giving consent to continue in this extension phase. That means the population in the extension phase is a subpopulation of the control arm of the main study.

4.1. Demographics and Baseline Characteristics

For both main study and extension phase, demographic and screening/baseline characteristics will be tabulated and summarized with descriptive statistics per vaccine intervention arm and over all participants. The following demographic and baseline characteristics will be summarized.

- Sex (Female/Male)
- Age (months)
- Race
- Ethnicity
- Height (Body length in cm)
- Weight (kg)
- Baseline EBOV-GP binding antibody response (EU/mL) status.
- Weight-for-age percentile at baseline, using WHO Child Growth Standards (birth to 24 months)⁴.

To obtain the weight-for-age percentile for the participants, the z-score (z) will first be determined as:

$$z = \frac{\left(\left(\frac{weight}{M}\right)^{L} - 1\right)}{(S \times L)}.$$

Where L, M and S denote the power in the Box-Cox transformation, median and generalized coefficient of variation, respectively. The L, M and S are the values from the appropriate WHO table⁴ corresponding to the age in months of the child. The percentile corresponding to the calculated z-score will then be obtained based on the Standard Normal distribution.

For example, to obtain the weight-for-age z-score of a 4-month-old male who weighs 7.5 kg, the L, M and S values from the appropriate (Weight-for-age tables: WHO Child Growth Standards Data File⁴) table are L= 0.1553, M=7.0023, and S=0.11316. Using the above formula, the calculated z-score for this child is 0.4173029. This z-score corresponds to the 66th percentile.

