4.1.2. Exclusion Criteria

Any potential participant who meets any of the following criteria will be excluded from participating in the study:

- 1. Having received any candidate or other Ebola vaccine.
- 2. History of EVD, or prior exposure to Ebola virus, including travel to an area with a current Ebola outbreak less than 1 month prior to screening.
- 3. Having received any experimental candidate Ad26- or MVA-based vaccine in the past.

 Note: Receipt of any approved vaccinia/smallpox vaccine or experimental Ad-vector vaccine other than Ad26 prior to study entry is allowed.
- 4. Criterion modified per Amendment 2
 - 4.1 Known allergy or history of anaphylaxis or other serious adverse reactions to vaccines or vaccine products (including any of the constituents of the study vaccines [eg, polysorbate 80, ethylenediaminetetraacetic acid (EDTA) or Lhistidine for Ad26.ZEBOV vaccine; tris (hydroxymethyl)-amino methane

(THAM) for MVA-BN-Filo vaccine and *Neisseria meningitidis* polysaccharide or tetanus toxoid for MenACWY]), including known allergy to chicken or egg proteins and aminoglycosides (gentamicin).

- 5. Criterion modified per Amendment 2
 - 5.1 Presence of acute illness (this does not include minor illnesses such as mild diarrhea or mild upper respiratory tract infection) or axillary temperature ≥37.5°C on Day 1. Participants with such symptoms will be excluded from enrollment at that time but may be rescheduled for enrollment at a later date.
- 6. Weight-for-age z-scores below -2 standard deviations of normal for age according to the WHO growth charts (<1-year-olds).²¹
- 7. Having been vaccinated with any live-attenuated vaccine within 30 days before the first vaccination, and with any inactivated vaccine within 15 days before the first vaccination.
 - Note: Study intervention administration may be rescheduled to allow for infants to receive their routine immunizations and be able to participate in this study.
- 8. Major congenital anomalies or known genetic disorders, which in the opinion of the investigator or other delegated individual would increase the risk of an adverse outcome from participation in the study.
- 9. Infant lives in an orphanage or other institution.
- 10. Significant prematurity or antenatal, perinatal, or early postnatal complications as judged by the investigator or other delegated individuals.

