11.3. Participant Information

For all participants, demographic characteristics (eg, age, weight and length percentiles according to WHO pediatric growth and weight charts, ²¹ race, and gender), and other baseline characteristics (eg, vital signs, concomitant diseases) will be tabulated and summarized with descriptive statistics.

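### Does the weight-for-age worked example in SAP 4.1, whose stated z-score does not follow from its printed inputs, call for a change to the plan?

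*SAP*

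**What the plan says.** SAP 4.1 (Demographics and Baseline Characteristics) lists weight-for-age percentile at baseline among the characteristics to be summarized in both the main study and the extension phase. The derivation has three parts.

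- The z-score is ((weight/M)^L − 1)/(S × L), where "L, M and S denote the power in the Box-Cox transformation, median and generalized coefficient of variation".
- The parameters are looked up for the child's age: "The L, M and S are the values from the appropriate WHO table".
- The z-score is then converted: "The percentile corresponding to the calculated z-score will then be obtained based on the Standard Normal distribution".

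An illustration follows, for "a 4-month-old male who weighs 7.5 kg". The parameters are printed as "L= 0.1553, M=7.0023, and S=0.11316", and the outcome is given as: "Using the above formula, the calculated z-score for this child is 0.4173029. This z-score corresponds to the 66th percentile".

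Protocol 11.3 (Participant Information) asks for "weight and length percentiles according to WHO pediatric growth and weight charts" as part of the descriptive baseline summary. The same WHO measure appears in Protocol 4.1.2 as an exclusion criterion: "Weight-for-age z-scores below -2 standard deviations of normal for age according to the WHO growth charts". Protocol 4.2.2 has the corresponding criterion for the extension phase.

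**The concern.** A reader who puts the printed numbers into the printed formula does not get the printed answer, and the gap is far larger than rounding. This is the only numerical illustration the SAP gives for the derivation, so a programmer might use it to test code. If 7.0023 is the right median, correct code would fail to reproduce the example, and code holding 7.1553 for 4-month-old boys would reproduce it. In that case the reported percentiles for those boys would be too low. Because the study also screens on the WHO weight-for-age z-score, one might further wonder whether eligibility is touched.

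**Working it through.** **Inputs**, all from SAP 4.1: weight 7.5 kg, L = 0.1553, M = 7.0023, S = 0.11316. Stated result: z = 0.4173029, 66th percentile.

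**Step 1. The example as printed.**

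- weight/M = 7.5/7.0023 = 1.071077
- (1.071077)^0.1553 − 1 = 0.010721
- S × L = 0.11316 × 0.1553 = 0.017574
- z = 0.010721/0.017574 = 0.6100
- Φ(0.6100) = 0.7291, the 73rd percentile

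The plan's figure is not reproduced. The gap is 0.6100 − 0.4173 = 0.1927 SD, and 72.91 − 66.18 = 6.73 percentile points.

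**Step 2. The conversion from z to percentile.** Φ(0.4173029) = 0.6618, the 66th percentile. This step is sound, so the mismatch lies between the inputs and z.

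**Step 3. Rounding and alternative readings of the formula.**

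| Variant | z |
|---|---|
| L, M, S anywhere within their rounding | 0.60995 to 0.61013 |
| As above, with weight 7.45 to 7.55 kg | 0.550 to 0.670 |
| Log form (L tending to 0) | 0.6068 |
| Linear form | 0.6281 |
| L and S exchanged | 0.4439 |
| Misplaced brackets | 0.0147, 0.0947 or 53.7 |

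None gives 0.4173.

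**Step 4. Which single input would give the stated z?** Each was solved for with the others held as printed.

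| Input changed | Exact solution | z at the input's printed precision |
|---|---|---|
| M | 7.1553000 | 7.1553 gives 0.41730285 |
| Weight | 7.3396 kg | 7.3 kg gives 0.3691 |
| S | 0.165424 | 0.16542 gives 0.4173121 |
| L | −11.68096 | −11.6810 gives 0.4173024 |

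Only M lands on the stated figure: 0.41730285 rounds to 0.4173029. The adjacent values M = 7.1552 and M = 7.1554 give 0.4174273 and 0.4171784, which do not. In full, with M = 7.1553: 7.5/7.1553 = 1.048174; (1.048174)^0.1553 − 1 = 0.0073336; 0.0073336/0.017574 = 0.4173.

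The illustration was therefore most likely computed with M = 7.1553. The decimals .1553 are also those of the printed L, which hints at a copying slip. The WHO table is not part of the documents, so they cannot show which M is right.

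**Step 5. What depends on the example.** The SAP tells the analyst to take L, M and S from the WHO table by age and to apply the formula. None of the example's numbers enters that instruction. The output is a descriptive baseline summary, and weight in kilograms is summarized separately. SAP 1.3 and Protocol 2.2 state that no formal hypothesis testing is planned. The exclusion criteria in Protocol 4.1.2 and 4.2.2 refer to the WHO growth charts and not to the SAP. If the slip is confined to the illustration, the number of participants affected is 0.

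**The case for a change.** The strongest argument for acting is that a printed statement in the SAP is wrong and the remedy is one sentence. The seven-decimal match also shows that a calculation with M = 7.1553 was probably carried out somewhere, so the value might sit in a program's look-up row. If it did, and if 7.0023 is the right median, z-scores for 4-month-old boys would be too low by 0.184 SD (at a true z of −2) to 0.197 SD (at +2), and their percentiles by up to about 7.6 points. Assuming ages spread evenly over the eight months from 4 to under 12 and half the infants boys, that would concern about 107/8/2 = 6.7 infants, or roughly 3 to 13 if that share is halved or doubled.

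The inconsistency itself stands. The consequences rest on conditions the documents do not support:

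- Nothing describes the example as a validation case or says that a program was or will be tested against it.
- Nothing indicates that the look-up row differs from the WHO table.
- The direction of any bias depends on 7.0023 being right. If 7.1553 is the table value, the stated z is right, only the printed M is wrong, and correct code reproduces the example.
- M = 7.1553 is the simplest explanation but not the only possible one. Changing two inputs together can also give the stated z: a scan of M from 6.0 to 7.5 with S from 0.05 to 0.25, at printed precision, finds 17 pairs that do so.

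The link to eligibility does not hold, because no text has sites using the SAP example for screening.

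**Conclusion.** The observation is correct: the printed inputs give z = 0.610 and the 73rd percentile, against the stated 0.4173029 and 66th, a difference of 0.193 SD or 6.7 percentile points within the illustration. It is a clerical slip and does not call for a change to the plan. An analyst who follows SAP 4.1 as written, with the formula and the WHO table values by age, obtains the right percentile whatever the example says. Correcting the example would alter no participant's value, no summary table and no conclusion.

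This rests on one assumption, that programmers take L, M and S from the cited WHO table as instructed and do not copy them from the illustration. The documents give no reason to doubt it. A programmer who compares code with the example will notice the mismatch and can settle it by looking up M for a 4-month-old boy in that table, which is ordinary programming practice.

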4.2. Disposition Information

For both main study and extension phase, the number and percentage of participants screened, participants in the full analysis set, participants vaccinated but not randomized, participants randomized but not vaccinated, participants who received MenACWY as third vaccination, participants who completed (study completion and vaccination completion) and discontinued participants (study discontinuation and vaccination discontinuation) with the reason of discontinuation will be tabulated per intervention arm and overall. Also, the number of participants and percentage in each analysis period will be tabulated.

4.3. Treatment Compliance

For both main study and extension phase, the number and percentage of participants receiving the second vaccination within the protocol defined windows will be summarized.

4.4. **Protocol Deviations**

For both main study and extension phase, major protocol deviations will be summarized by deviation category. A listing of the major protocol deviations will also be generated. The deviations that have the potential to influence immune response will be flagged in the listing.

4.5. Concomitant Medications

The analysis of concomitant therapies will be done using the World Health Organization (WHO) drug coding terms. If the coded term for a concomitant medication is missing, then the reported term will be used and flagged in the table. For both main study and extension phase, the concomitant therapies will be tabulated per analysis period. Additionally, a listing of all pre-study and concomitant therapies will be provided. There will be special attention to analgesics/antipyretics (such as acetaminophen, non-steroidal anti-inflammatory drugs [NSAIDs] and aspirin) administered during the first 8 days (including the day of the vaccination) following each vaccination.

Based on their start and stop date, concomitant therapies will be reported in each applicable analysis period. If a concomitant therapy record misses components of its start and/or stop dates (day and/or month and/or year), then they will be assigned as follows:

- In case of partial start or stop dates, the concomitant therapy records will be allocated to periods using the available partial information, without imputations. If, for example, only month and year are available, these will be compared to the month and the year of the periods, and the concomitant therapy record will be allocated to the period(s) where these date parts match. This rule may lead to assignment to multiple periods.
- In case of a completely missing start date, the concomitant therapy will be considered as having started before the trial.
- In case of a completely missing end date, the concomitant therapy will be considered as ongoing at the end of the trial.

Remark: In addition to the date information, time information is considered to allocate concomitant therapies to analysis periods, if available.

5. SAFETY

Safety analyses will be performed on the full analysis set. Continuous variables will be summarized using the following statistics, as appropriate: number of observations, arithmetic mean (mean), 95% CI for the mean, standard deviation (SD), standard error (SE), median, quartiles (Q1 and Q3), minimum and maximum. Frequencies and percentages (one decimal place) will be generated for categorical variables. No formal comparisons between groups will be provided.

The safety data will be presented by vaccine regimens (ie, intervention arms) as described in the study protocol. The data will be presented by analysis period (post-dose 1 and post-dose 2) as well as over the entire regimen period (ie, combined post-dose 1 and post-dose 2 periods). Denominator for the percentages will be the number of participants in the considered population and period/phase for a certain regimen (eg, incidence per 100 participants/period).

5.1. Adverse Events (AE)

5.1.1. Definitions

Solicited AEs shown in the tables will be extracted from the investigator assessment pages of the eCRF. For unsolicited AEs, only the AEs within the 28-day period following each vaccination will be presented in the safety tables except for SAE, which will be captured and tabulated in the outputs covering the entire study duration. A listing will also be generated for all collected unsolicited adverse events.

Solicited local AEs will be considered (by definition) as related to the study vaccine. The severity of the AEs will be classified as Grade 1 to 4. In case no grades are available, the grading of the solicited events will occur according to the grading list in Attachment 1.

The main study outputs will present AEs for both the Ebola vaccination regimen as the control arm. At the end of the extension phase, AEs are presented for the participants of the control arm receiving the Ebola vaccination regimen. Listings will show all AEs of both parts of the study, adding a column showing main study/extension phase. Tabulations will be done for each phase separately.

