6.2. Contraindications to Second Vaccination and 6-months Post-dose-2 Vaccination

A participant will not be given the second vaccination or the MenACWY vaccination at 6 months post-dose-2 if he/she experiences any of the following events at any time after the first vaccination:

- 1. Anaphylaxis clearly attributable to vaccination with study intervention; OR
- 2. Generalized urticaria within 24 hours of vaccination considered to be related to study intervention; *OR*
- 3. A serious adverse event considered to be related to study intervention; OR
- 4. Injection site ulceration, abscess, or necrosis considered to be related to study intervention; OR
- 5. Any other safety concern threatening the participant's safety.

Participants experiencing any of the events described above must not receive any further study intervention but should be monitored for safety and for immunogenicity according to the protocol.

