10.2. Discontinuation of Study Intervention/Withdrawal From the Study

Discontinuation of Study Intervention

A participant will not be automatically withdrawn from the study if he or she has to discontinue study intervention before the end of the intervention regimen.

A participant's study intervention (dose 1 or dose 2) must be discontinued at the discretion of the investigator and after consultation with the sponsor for any of the events in Section 6.1.

A participant's study intervention should be **permanently** discontinued if:

- The investigator believes that for safety reasons (eg, adverse event) it is in the best interest of the participant to discontinue study intervention;
- Confirmed EVD
- The participant experiences any of the events described in Section 6.2;
- The randomization code is broken by the investigator or the study-site personnel (only applicable for main study).

Participants meeting any of the reasons listed above must not receive any further study intervention, but should continue to be monitored for safety and immunogenicity according to the protocol if this does not result in safety risks for the participant. In case of early discontinuation of study intervention due to an adverse event, the investigator will collect all information relevant to the adverse event and safety of the participant, and will follow the participant to resolution, or until reaching a clinically stable endpoint. In case of a study pause, participants need to follow procedures as described in Section 9.2.

Withdrawal From the Study

Parent(s)/guardian have the right to withdraw their child from the study at any time for any reason without affecting the right to treatment by the investigator. The investigator should make an attempt to contact participants who did not return for scheduled visits or follow-up. Although parent(s)/guardian are not obliged to give reason(s) for withdrawing prematurely, the investigator should make a reasonable effort to ascertain the reason(s) while fully respecting the participant's rights.

A participant will be withdrawn from the study for any of the following reasons:

- Lost to follow-up
- Withdrawal of consent
- Death
- Repeated failure to comply with protocol requirements
- Decision by the sponsor or the investigator to stop or cancel the study
- Decision by local regulatory authorities or IEC/IRB to stop or cancel the study

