12.3. Procedures

12.3.1. All Adverse Events

Symptoms of solicited local and systemic adverse events will be collected in the diary in the evening after the first and second vaccination and then daily for the next 7 days. Unsolicited adverse events will be reported from the first vaccination until 28 days post-dose-1, and from the second vaccination until 28 days post-dose-2.

Serious adverse events and/or special reporting situations that are related to study procedures or that are related to non-investigational (concomitant) sponsor products will be reported from the time a signed and dated ICF is obtained onwards until the end of the study. All other serious adverse events and/or special reporting situations will be reported from the day of the first vaccination onwards until 6 months post-dose-2 in the main study and until 28 days post-dose-2 in the extension phase. The sponsor will evaluate any safety information that is spontaneously reported by an investigator beyond the time frame specified in the protocol.

The investigator will monitor and analyze the study data including all adverse event and clinical laboratory data as they become available and will make determinations regarding the severity of the adverse experiences and their relation to study intervention. All adverse events will be deemed related to study intervention or not related to study intervention, according to Section 12.1.2.

The investigator or clinical designee must review both post-injection reactogenicity and other adverse event CRFs to insure the prompt and complete identification of all events that require expedited reporting as serious adverse events, invoke pausing rules or are other serious and unexpected events.

All adverse events, regardless of seriousness, severity, or presumed relationship to study intervention, must be recorded using medical terminology in the source document and the CRF. Whenever possible, diagnoses should be given when signs and symptoms are due to a common

etiology (eg, cough, runny nose, sneezing, sore throat, and head congestion should be reported as "upper respiratory infection"). Investigators must record in the CRF their opinion concerning the relationship of the adverse event to study therapy. All measures required for adverse event management must be recorded in the source document and reported according to sponsor instructions.

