2.1. Analysis Periods/Phases

Because the analysis of adverse events (AEs) will be presented per period (and not per time point), these will be assigned to the analysis periods based on Table 3 for the main study, and on Table 4 for the extension phase.

For the analysis that will be presented by time point (e.g. immunogenicity data), the electronic case report form (eCRF) visit schedules will be used for the post baseline assessments as follows:

- For the analysis based on the per protocol set, only assessments that fall within the protocol defined visit window will be used.
- For other analyses based on the full analysis set (if applicable), the assessments that fall outside the protocol defined windows will also be included. If only unscheduled visits are present for a time point, then the one closest to the scheduled visit will be used. If distances of multiple assessments to the scheduled visit are equal, the measurement with the latest date will be used.

		Interval			
Phase	Period	From	То		
Screening		Date and time of signing the informed consent form	One minute prior to start of post dose 1 period		
Regimen	Post-dose 1	Date and time of first vaccination	 Minimum of: a) 23:59 on the date of last contact (for early discontinuation) b) 23:59 on the date of database cut-off date in case of interim c) 23:59 of 28 days after the first vaccination (23:59 of day of vaccination + 28 days) d) One minute prior to post-dose 2 period 		
Follow-up 1		One minute after post-dose 1 period ends	 Minimum of: a) 23:59 on the date of last contact (for early discontinuation) b) 23:59 on the date of database cut-off date in case of interim c) One minute prior to post-dose 2 period 		
Regimen	Post-dose 2	Date and time of second vaccination	 Minimum of: a) 23:59 on the date of last contact (for early discontinuation) b) 23:59 on the date of database cut-off in case of interim analysis c) 23:59 of 28 days after the second vaccination (23:59 of day of vaccination + 28 days) 		
Follow-up 2		One minute after post-dose 2 period ends	 Minimum of: a) 23:59 on the date of last contact (for early discontinuation) b) 23:59 on the date of database cut-off in case of interim analysis c) 23:59 on the date of last study visit 		

Table 3: Analysis Period Definitions (Main Study)

		Interval		
Phase	Period	From	То	
eFollow-up 2		One minute after Follow-	One minute prior to signing the informed consent	
		up 2 phase ends	form	

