5.1.2. Analysis of Adverse Events

Number and percentage of participants with at least one particular AE (unsolicited/solicited) will be tabulated. Unsolicited AEs will be summarized by System Organ Class and Preferred Term. Solicited AEs will be summarized by class (local, systemic) and preferred term.

The following tables will be generated for solicited AEs: summary, by worst severity grade, at least Grade 3, related (systemic only), time to onset (in days) and duration (in days) for most frequent events and body temperature. Note that duration is defined as number of days from the start of the event until resolution of the event. The time to first onset is defined as (date of first onset – reference date + 1). The reference date is the start date of the vaccination period.

For unsolicited AEs, the following tables will be generated: summary table (including SAE, AE with fatal outcome, AEs leading to study discontinuation, and AEs leading to discontinuation of study vaccination), all events, most frequent, grade 3, permanent stop of vaccination, related and SAE.

Listings and/or participant narratives will be provided as appropriate, for those participants who die, discontinue study vaccinations due to an AE, or experience a severe or serious AE.

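### The tables of AEs leading to discontinuation omit non-serious events that start after Day 29 and stop Dose 2, so they can undercount and disagree with disposition

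*SAP*

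**What the plan says.** **Which AEs enter the tables.** SAP 5.1.1 states: "For unsolicited AEs, only the AEs within the 28-day period following each vaccination will be presented in the safety tables except for SAE". SAEs are the only exception and are tabulated over the whole study. Protocol 11.4 carries the same 28-day onset limit. SAP section 5 presents safety data for post-dose 1, post-dose 2 and the two combined.

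**Which tables are planned.** The unsolicited-AE summary in SAP 5.1.2 includes "AEs leading to study discontinuation, and AEs leading to discontinuation of study vaccination", and there is a separate table of AEs that permanently stop vaccination. None of these is exempted from the limit.

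**How AEs are placed.** SAP 5.1.3 assigns an AE by its start date and time, not by the date of any decision that follows from it. SAP Table 3 closes post-dose 1 no later than "23:59 of 28 days after the first vaccination (23:59 of day of vaccination + 28 days". Follow-up 1 then begins "One minute after post-dose 1 period ends" and runs until Dose 2.

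**When a dose can be stopped.** Protocol 6.2 bars further vaccination "if he/she experiences any of the following events at any time after the first vaccination". Protocol 10.2 also lets the investigator stop for safety reasons, and Protocol 6.1 allows withdrawal from a dose because of acute illness or fever at the visit.

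**What else reports the stop.** SAP 4.2 tabulates vaccination and study discontinuation by reason and arm. SAP 5.1.1 lists every collected unsolicited AE. SAP 5.1.2 adds listings or narratives, as appropriate, for participants who stop vaccination because of an AE.

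**The concern.** A 28-day onset window suits an incidence table, because it matches the primary endpoint. It suits a table of AEs that stop vaccination less well, because Dose 2 is decided at Day 57 ±7, about four weeks after the window closes. A brief examination and a full blood count are scheduled before Dose 2. Abnormal examination findings after Dose 1, and clinically relevant laboratory changes, go onto the AE page. New reasons to withhold Dose 2 can therefore come to light at that visit, with onset after Day 29.

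Safety is the primary objective, and Protocol 11.2 says that AEs precluding further administration are not anticipated. When the expected count is near zero, one omitted case can turn a non-zero row into a zero. The same report could then show an infant discontinued for an AE in disposition and none in the AE tables.

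**Working it through.** **Inputs.** Dose 1 is on Day 1, and post-dose 1 ends on the day of vaccination + 28 days (SAP Table 3). Dose 2 is due on Day 57 ±7 (Protocol Time and Events Schedule). Postponement of up to 10 days beyond the window is allowed (Protocol 6.1). The planned arms are 73 and 34 (Protocol Table 2).

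**Step 1: the SAP's own cut-off.** 1 + 28 = Day 29, ending at 23:59. The first onset day outside the window is Day 30.

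**Step 2: length of the untabulated interval.** If Dose 2 falls on Day D, the full days from Day 30 to the day before Dose 2 number D − 30, out of D − 1 days since Dose 1.

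| Dose 2 day | D − 30 | D − 1 | Share |
|---|---|---|---|
| 50 (earliest in window) | 20 | 49 | 41% |
| 57 (planned) | 27 | 56 | 48% |
| 64 (latest in window) | 34 | 63 | 54% |
| 74 (64 + 10, postponed) | 44 | 73 | 60% |

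The hours before the dose on the visit day itself also fall in Follow-up 1.

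**Step 3: trace one case.** Take a non-serious AE that starts on Day 45 and leads to Dose 2 being withheld.
- By start date it belongs to Follow-up 1 (SAP 5.1.3 and Table 3).
- It is not within 28 days of a dose and is not an SAE, so SAP 5.1.1 keeps it out of the safety tables.
- Follow-up 1 is not among the periods presented in SAP section 5.
- It therefore appears neither in the discontinuation rows of the AE summary nor in the permanent-stop table.
- SAP 4.2 still counts the infant under reason for discontinuation, and the AE listing still shows the event.

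**Step 4: exceptions.** SAP Attachment 2 brings back a few such events. A partial start date may match more than one period. A wholly missing start date normally goes to post-dose 1. An event that overlaps or directly follows one of the same preferred term from the active period is merged into it. An ordinary late-onset event with a known start date is not recovered.

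**Step 5: weight of one infant.** 1/73 = 1.4 percentage points in the vaccine arm; 1/34 = 2.9 in control.

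**Step 6: expected number.** The documents give no rate. Purely as an assumption for scale, if 1% to 5% of the 107 infants had such an event, the count would be 107 × 0.01 = 1.07 to 107 × 0.05 = 5.35, or about 1 to 5 infants.

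**The case against.** The best defence is that the SAP carries out a prespecified rule. The primary endpoint covers unsolicited AEs to 28 days after each dose, and Protocol 11.4 limits the analysis in the same way. That stands for the incidence tables. It also means that editing SAP 5.1.1 alone would put the SAP at odds with the protocol.

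The pool of affected events is also small. Among the events in Protocol 6.2, related SAEs are exempt from the limit and urticaria is defined within 24 hours of vaccination. Nothing in the documents suggests that the other named, vaccine-attributed events would start more than 28 days after a dose. Acute illness or fever at the visit may lead only to postponement. What remains is mainly the open-ended safety criterion, investigator judgement under Protocol 10.2, and withdrawal from a dose under Protocol 6.1. This limits the likely count but does not make it zero.

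Four stronger readings are tempting, and the documents do not support them:
- *The event is lost from the report.* It is not: disposition, listings and, as appropriate, narratives show it. But listings give no rate by arm, and disposition as planned gives the reason without the AE term.
- *The omission favours one arm.* No figure in either document points to a difference in late-onset events.
- *The gap before the third vaccination is just as serious.* Post-dose 2 closes on Day 57 + 28 = Day 85, leaving Days 86 to 236, or 151 days, before the Day 237 visit. But that dose is MenACWY in both arms, the pausing rules do not apply to it, and the primary objective concerns the two-dose regimen.
- *These AEs would not be collected.* Protocol 12.3.1 does say "Unsolicited adverse events will be reported from the first vaccination until 28 days post-dose-1, and from the second vaccination until 28 days post-dose-2". The same section also requires all AEs to be recorded in the CRF, and Protocol 10.2 adds: "In case of early discontinuation of study intervention due to an adverse event, the investigator will collect all information relevant to the adverse event". Together these largely cover collection.

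**Conclusion.** The point holds for non-serious unsolicited AEs. As written, one that starts from Day 30 up to the Dose 2 visit and stops Dose 2 is left out of the tables of AEs leading to discontinuation. The interval is 27 full days for Dose 2 on Day 57, 20 to 34 across the window and up to 44 with postponement.

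The consequence is an undercounted table that can disagree with disposition, not a hidden safety event. The size in infants cannot be derived from the documents; each omitted infant is worth 1.4 or 2.9 percentage points, depending on arm. The conclusion assumes that the onset limit is applied literally to every unsolicited-AE table, as SAP 5.1.1 reads, and that the event has a known start date. It should be corrected before the tables are programmed, but it does not threaten the primary 28-day analysis.

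**What to change.** 1. In SAP 5.1.1, widen the exception to: *except for SAEs and AEs leading to discontinuation of study vaccination or of the study, which are tabulated by arm over the entire study phase regardless of onset period*.
2. Put the same exception into the period-based presentation in SAP section 5 and into Protocol 11.4, so that the documents agree.
3. Keep the 28-day limit for the incidence tables.
4. Cross-check the discontinuation tables against the reasons tabulated under SAP 4.2 and explain any difference.
5. Optionally, add a sentence to Protocol 12.3.1 that an AE leading to discontinuation is recorded whenever it starts. This is mostly clarification.

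The cost is a clause in each of three places and a few table rows. The downside is that a few late, possibly unrelated events will appear in the discontinuation tables. No dose, schedule or stopping rule changes.
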